4.3. Concomitant medication and treatment

In addition to abatacept, patients receive permitted conventional DMARDs at a stable pre-entry dose. The dose of DMARDs at entry into the study should be continued without change during the study. Oral corticosteroid (5mg/day prednisone or equivalent) and NSAIDs are permitted during the study if the dose has been stable.

4.4. Premature withdrawal

Patients have the right to withdraw from the study at any time for any reason. All patients who withdraw from the study must return to the clinic for a complete final evaluation 1 week following the last dose of study drug.

5. Study Drug/Treatment

5.1. Investigational Product

The investigational medicinal product (IP) for this study is subcutaneous abatacept 125mg once weekly for 24 weeks. All study participants will take abatacept in combination with standard of care anti-rheumatic background therapy, including DMARDs.

5.2. Storage, Administration, and Destruction of Investigational Product

The sponsor, BMS, will provide the IP, abatacept, to the study site for use as specified in this study. Background therapy, including DMARDs, and anti-rheumatic therapies will not be provided by the study. IP will be stored in accordance with the package insert at Investigational Drug Services (IDS), a secure pharmacy. IDS will maintain a record of all IP received, including inventory and dispensation records. Study participants will be instructed to dispose of used IP in accordance with community standards or to return used IP to the site for destruction. If study participants return used IP to the study site, IDS will ensure destruction of used IP in accordance with established institutional policies.

IP will be dispensed only to study subjects who have met all the required eligibility criteria and are enrolled in the study. Participants will take their first and last dose of IP in the clinic. Participants are expected to take their study medication in the clinic at Day 0, Week 6, Week 14, and Week 24. All other study medication may be taken at home.

6. Study procedures

Table 6.1-1 Schedule of Assessments

Procedure	Baseline/Day 0 Visit	Week 6 Visit	Week 14 Visit	Week 24 Visit	Post Treatment 4 Week Follow Up (Telephone)	Post Treatment 15 Week Follow Up (Telephone)
Visit Window		+/- 5 days	+/- 5 days	+/- 5 days	+/- 5 days	+2 weeks
Informed Consent	x					
Eligibility Review	x					
Patient Self-Assessments						
MDHAQ	x	x	x	x		
Patient Global Assessment	x	x	x	x		
FACIT-F	x	x	x	x		
SF-12	x	x	x	x		
Physician Assessments						
Physician Global Assessment	x	x	x	x		
Symptom Targeted Physical Exam	x	x	x	x		
Complete Physical Exam	x					
Joint Exam	x	x	x	x		
Study Procedures						
Biomarker Blood Draw	x	x	x	x		
Laboratory Tests: CBC, CMP, ESR, CRP, Immunoglobulins A, G, M	x	x	x	x		
Vital Signs	x	x	x	x		
Height	x					
Ultrasound Exam	x		x	x		
Adverse Event Review	x	x	x	x	x	x
Medication Review	x	x	x	x	x	
Investigational Product Dispensation	x	x	x			
In clinic IP administration	x	x	x	x (Last Study Dose)		
Urine Pregnancy Test (WOCBP only)	x					

Baseline visit (Day 0)

The following procedures and assessments are to be completed during the baseline visit.

- Informed consent
- Review patient eligibility and ensure that all inclusion and exclusion criteria are met
- Patient self-assessment measures: MDHAQ, patient's global assessment, FACIT-F, SF-12
- Blood samples for laboratory tests: Complete Blood Count (CBC), Comprehensive Metabolic Panel (CMP), Erythrocyte Sedimentation Rate (ESR), C Reactive Protein (CRP), IgG, IgM and IgA rheumatoid factor, IgG and IgA anti-CCP, Immunoglobulins G, M, A
- Biomarker blood draw (serum, PBMC)
- Joint exam
- Complete physical exam
- Vitals signs: blood pressure, pulse, temperature, weight, height
- Physician's global assessment
- Physician safety assessment
- Ultrasound exam
- Adverse event review
- Medication review
- For women of childbearing potential, a urine pregnancy test should be completed prior to dispensing study medication
- Study drug (abatacept) dispensation and in clinic injection

Treatment visit (Weeks 6, 14, 24)

Patients must return to the clinic for assessments at weeks 6, 14 and 24. The following procedures and assessments are to be completed during the treatment visits.

- Patient self-assessment measures: MDHAQ, PGA, FACIT-F, SF-12
- Blood samples for laboratory tests: Complete Blood Count (CBC), Comprehensive Metabolic Panel (CMP), Erythrocyte Sedimentation Rate (ESR), C Reactive Protein (CRP), IgG, IgM and IgA rheumatoid factor, IgG and IgA anti-CCP, Immunoglobulins G, M, A
- Biomarker blood draw (serum, PBMC)
- Joint exam

- Symptom targeted physical exam
- Vital signs including blood pressure, pulse, temperature, and weight
- Physician's global assessment
- Physician safety assessment
- Ultrasound exam (weeks 14 and 24)
- Adverse event review
- Medication review
- Study drug (abatacept) dispensation and in clinic injection

Follow-up telephone contact (4 & 15 weeks after the final treatment visit)

Patients receive a follow-up phone call from study personnel 4 weeks and 15 weeks after the week 24 visit. Patients who discontinue from the study early will have telephone visits at 4 weeks and 15 weeks after their end of treatment visit, if continued follow up is acceptable. The following procedures and assessments are to be completed at the follow-up telephone contact.

- Follow-up on transition to standard of care (PT Week 4 only)
- Follow-up on any adverse events

7. Safety and Reporting

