4.2. Eligibility

Inclusion Criteria

1. Male or non-pregnant, non-nursing female
2. Age ≥ 18 years
3. Body weight ≤ 120 kg
4. Classification of RA according to the 1987 ACR criteria or 2010 ACR/EULAR criteria
5. Symptoms of RA present for at least 3 months and **less than 10 years** prior to screening
6. Clinical Disease Activity Index (CDAI) ≥ 16 corresponding to moderate to severe disease activity
7. Patients taking oral DMARDs must be on stable doses of DMARDs for at least 4 weeks prior to abatacept initiation
8. Treatment within the past year with either methotrexate (MTX), leflunomide (LEF), hydroxychloroquine (HCQ) and/or sulfasalazine (SSZ) for ≥ 8 weeks
9. Patient who have received one prior anti-TNF must have discontinued etanercept, infliximab, adalimumab, certolizumab, or golimumab for at least 6 months prior to screening
10. Patients taking oral corticosteroid, the dose must be ≤ 5 mg/day prednisone or equivalent
11. Females of childbearing potential and males with female partners of childbearing potential may participate in this study only if using a reliable means of contraception

Exclusion Criteria

1. Previous treatment with abatacept
2. Previous treatment with rituximab, tocilizumab, tofacitinib, sarilumab or anakinra
3. Previous treatment with IV immunoglobulin, plasmapheresis, alkylating agents such as cyclophosphamide
4. Intraarticular or parenteral corticosteroids within 4 weeks of screening
5. Rheumatic autoimmune disease other than RA including systemic lupus erythematosus, primary Sjogren syndrome, spondyloarthritis, systemic sclerosis, dermatomyositis, mixed connective tissue disease, vasculitis
6. Non-rheumatic autoimmune disease including inflammatory bowel disease, psoriasis, multiple sclerosis
7. Recurrent or chronic bacterial, viral, fungal, mycobacterial or other infections including HIV, Hepatitis B or C, latent TB (TB not adequately treated according to guidelines)
8. Primary or secondary immunodeficiency
9. Current uncontrolled renal, gastrointestinal, endocrine, pulmonary, cardiac, or neurologic disease
10. History of malignancy within 10 years prior to screening, except for appropriately treated carcinoma in situ of the cervix and non-melanoma skin carcinoma
11. History of alcohol, drug or chemical abuse within 1 year prior to screening
12. Laboratory exclusion criteria at screening including
 - eGFR <30 ml/min
 - ALT or AST >1.5 times upper limit of normal

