13. Major surgery (including joint surgery) within 8 weeks prior to screening or planned major surgery during the study
14. Immunization with a live/attenuated vaccine within 4 weeks prior to screening
15. Pregnant or nursing women, or women of child bearing potential who plan to become pregnant prior to 14 weeks after the last dose of abatacept treatment.
16. Patients of reproductive potential not willing to use an effective method of contraception
17. Prisoners, or subjects who are compulsory detained

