7.3. Pregnancy

If it is discovered a patient is pregnant or may have been pregnant at the time of exposure to IP associated with this study, the pregnancy, AE's associated with maternal exposure and pregnancy will be reported to BMS within 24 hours of the site becoming aware. Every effort should be made to obtain follow up and pregnancy outcomes date for one year following the birth of the offspring.

Any pregnancy that occurs in a female partner of a male study participant should be reported to BMS within 24 hours of the study site becoming aware.

Study participants who become pregnant during the study will have study treatment discontinued. The treating physician or study investigator will council the study participant on potential risks and treatment options available.

Pregnancy Email Address: [contact]

Pregnancy [contact]

8. Statistical Analysis

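### The only scheduled pregnancy test is on Day 0; none precedes the further dispensing of abatacept at weeks 6 and 14

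*Combined protocol and SAP*

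**What the plan says.** Section 6, Table 6.1-1, has a row "Urine Pregnancy Test (WOCBP only" marked in the Day 0 column only. The row "Investigational Product Dispensation" is marked on Day 0, at week 6 and at week 14.

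The visit lists that follow the table agree with it. The baseline list says that, for women of childbearing potential, "a urine pregnancy test should be completed prior to dispensing study medication". The list for weeks 6, 14 and 24 includes dispensing and an in-clinic injection but no pregnancy test. It does include an item "Physician safety assessment", together with a targeted examination, an adverse event review and a medication review.

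Section 5.2 places the doses on Day 0 and at weeks 6, 14 and 24 in the clinic and then states: "All other study medication may be taken at home".

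Two other sections bear on the point:

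- Section 4.2, inclusion criterion 11: women of childbearing potential, and men with such partners, "may participate in this study only if using a reliable means of contraception". Exclusion criterion 15 covers pregnant or nursing women and "women of child bearing potential who plan to become pregnant prior to 14 weeks after the last dose of abatacept treatment". Exclusion criterion 16 covers unwillingness to use contraception.
- Section 7.3: "Study participants who become pregnant during the study will have study treatment discontinued".

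**The concern.** The protocol has a stopping rule for pregnancy but no scheduled way of finding one after the first dose. Section 7.3 acts once a pregnancy has come to light. Before the first supply, the protocol does not rely on contraception alone and requires a test as well. Before the second and third supplies it requires none, although the week 14 supply covers home dosing up to week 24.

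A site that follows the schedule exactly could therefore hand abatacept at week 6 or week 14 to a participant whose pregnancy neither she nor the clinician has noticed. What is at stake is avoidable fetal exposure in a participant who, under section 7.3, should have stopped treatment. The ROC analysis and the sample size of 25 are not at stake.

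**Working it through.** **1. Schedule compared with dispensing (Table 6.1-1 and the visit lists in section 6)**

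| Visit | Dispensing | Pregnancy test | Age of last test (visit window ±5 days) |
|---|---|---|---|
| Day 0 | yes | yes | same day |
| Week 6 | yes | no | 42 days (37–47) |
| Week 14 | yes | no | 98 days (93–103) |
| Week 24 | not marked; last dose in clinic | no | 168 days (163–173) |

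There is one scheduled test for three dispensing visits. The table and the two visit lists agree, so the blank cells are unlikely to come from the conversion of the PDF. The eligibility review, which covers non-pregnancy, is also marked on Day 0 only.

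**2. Longest untested interval on treatment**

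- Now: 24 weeks; at the window extreme, (168 + 5)/7 = 24.7 weeks.
- With tests at weeks 6 and 14: max(6, 14 − 6, 24 − 14) = max(6, 8, 10) = 10 weeks; at the window extreme, (173 − 93)/7 = 11.4 weeks.

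**3. Drug exposure after conception**

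The documents give no timing inputs, so the following are assumptions:

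- Conception time *t* is uniform over weeks 0 to 24.
- Without testing, the pregnancy is recognised *R* weeks after conception, with *R* = 4, 6 or 8.
- A urine test is positive from *L* weeks after conception, with *L* = 2 or 4.
- Drug stops at the earliest of *t* + *R*, week 24, or the first scheduled test at least *L* weeks after *t*.

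Mean exposure without further tests is [(24 − *R*)·*R* + *R*²/2]/24:

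- *R* = 4: (20×4 + 8)/24 = 3.67 weeks
- *R* = 6: (18×6 + 18)/24 = 5.25 weeks
- *R* = 8: (16×8 + 32)/24 = 6.67 weeks

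The mean saving is the sum of two areas divided by 24. The first area is for conceptions caught by the week 6 test (*t* ≤ 6 − *L*), where the saving is max(0, *R* − (6 − *t*)). The second is for those caught by the week 14 test (6 − *L* < *t* ≤ 14 − *L*), where it is max(0, *R* − (14 − *t*)).

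| *R* (weeks) | Saving, *L* = 2 | Saving, *L* = 4 | Mean exposure without tests | With tests |
|---|---|---|---|---|
| 4 | (2 + 2)/24 = 0.17 | 0 | 3.67 | 3.50–3.67 |
| 6 | (8 + 8)/24 = 0.67 | (2 + 2)/24 = 0.17 | 5.25 | 4.58–5.08 |
| 8 | (16 + 18)/24 = 1.42 | (6 + 8)/24 = 0.58 | 6.67 | 5.25–6.08 |

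The upper bound is a pregnancy not recognised at all during treatment. Mean exposure without tests is then 24/2 = 12.0 weeks. With tests it is (16 + 48 + 72)/24 = 5.67 weeks for *L* = 2 (saving 6.33) and (10 + 64 + 98)/24 = 7.17 weeks for *L* = 4 (saving 4.83).

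These are means per pregnancy. The documents do not give the number of women of childbearing potential or a pregnancy rate, so no study-level total can be calculated.

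**The case against.** The strongest reply is that this is a choice and not an error. Nothing in the documents promises repeat testing. The protocol has a coherent approach: test before first exposure, require contraception as a condition of taking part, exclude planned pregnancy until 14 weeks after the last dose, and stop and report if pregnancy occurs. Each treatment visit includes a physician safety assessment, a targeted examination and adverse event and medication reviews, any of which could prompt an unscheduled test. The consent pages are not in the public text, so what participants are told about reporting a suspected pregnancy cannot be judged. On realistic recognition times the saving is small, and adding two tests still leaves ten untested weeks, which is longer than either interval that the tests close.

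Most of this stands, and it limits the size of the point. It is a design gap and not a contradiction, the event should be uncommon, the benefit per pregnancy is modest, and testing frequency is a matter of degree. The figures for a never-recognised pregnancy are a bound and should not carry the argument.

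Two things do not follow. Clinical review at a visit helps only if someone suspects pregnancy, and the gap concerns pregnancies that nobody suspects. And contraception cannot be the full answer at weeks 6 and 14 when the protocol did not accept it as sufficient on Day 0. The Day 0 instruction to test before dispensing could perhaps be read as covering every dispensing. It appears only in the baseline list, however, and the later table cells are blank, so if that was the intent the table and the treatment-visit list still need the correction.

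**Conclusion.** The point holds, as a minor safety-monitoring gap. Two of the three dispensing visits have no pregnancy test, and at the second of them the only test is about 14 weeks old. That much comes directly from the schedule and rests on no assumption. The exposure saving does rest on assumptions about conception, recognition and test timing. It is 0.0 to 0.2 weeks per pregnancy for recognition at 4 weeks, 0.2 to 0.7 at 6 weeks and 0.6 to 1.4 at 8 weeks. The case for change is therefore not a large expected benefit. It is that a very cheap check would give the stopping rule in section 7.3 a scheduled trigger before each new supply.

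**What to change.** In Table 6.1-1, mark the urine pregnancy test for women of childbearing potential at weeks 6 and 14. Add it to the treatment-visit list for those two visits, to be done before dispensing, as on Day 0. State that after a positive result the in-clinic dose and the new supply are withheld and section 7.3 applies.

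The cost is two urine tests per woman of childbearing potential: at most 2 × 25 = 50 even if every subject were one. No new visit or blood draw is needed, and the sample size and analysis do not change. The ten weeks after the week 14 test would remain untested.

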7.1. Adverse events

An Adverse Event (AE) is defined as any new untoward medical occurrence or worsening of a preexisting medical condition in a clinical investigation participant administered study drug and that does not necessarily have a causal relationship with this treatment.

The causal relationship to study drug will be determined by a physician and will be used to assess all AE's. the causal relationship will be one of the following:

- Related: There is a reasonable causal relationship between study drug administration and the AE.
- Not Related: there is not a reasonable causal relationship between study drug administration and the AE.

All AE's will be documented from the point the informed consent is signed through 100 days post treatment.

7.2. Serious Adverse Events and Reportable Medical Events

A serious adverse event (SAE) is any untoward medical occurrence that:

- Results in death

- Is life threatening (defined as an event in which the participant was at risk of death at the time of the event; it does not refer to an event which hypothetically might have caused death if it were more severe)
- Requires inpatient hospitalization or causes prolongation of existing hospitalization
- Results in persistent or significant disability/incapacity
- Is a congenital anomaly or birth defect
- Is an important medical event (defined as a medical event(s) that may not be immediately life-threatening or result in death or hospitalization but, based upon appropriate medical and scientific judgement, may jeopardize the subject or may require intervention [eg, medical, surgical] to prevent one of the other serious outcomes listed in the definition above.)
- Suspected transmission of an infectious agent via the study drug is an SAE

Following the subject's written consent to participate in the study and through 100 days post study treatment, all SAE's, whether or not related to the IP or study procedures must be collected. All SAE's will be reported to BMS within 24 hours of the study site becoming aware of the event. All SAE's will be reported by fax transmission or reported via email.

SAE Email Address: [contact]

SAE [contact]

7.3. Pregnancy

If it is discovered a patient is pregnant or may have been pregnant at the time of exposure to IP associated with this study, the pregnancy, AE's associated with maternal exposure and pregnancy will be reported to BMS within 24 hours of the site becoming aware. Every effort should be made to obtain follow up and pregnancy outcomes date for one year following the birth of the offspring.

Any pregnancy that occurs in a female partner of a male study participant should be reported to BMS within 24 hours of the study site becoming aware.

Study participants who become pregnant during the study will have study treatment discontinued. The treating physician or study investigator will council the study participant on potential risks and treatment options available.

Pregnancy Email Address: [contact]

Pregnancy [contact]

8. Statistical Analysis

8.1. Study end points

8.1.1. Primary end point

- Baseline levels of T cell-associated biomarkers or other biomarkers predict ACR20 response with subcutaneous abatacept at week 14 [Time Frame: 14 weeks]

8.1.2. Secondary end points

- Baseline levels of T cell-associated biomarkers or other biomarkers predict ACR20 response predict ACR20 response with subcutaneous abatacept at week 24 [Time Frame: 24 weeks]
- Baseline levels of T cell-associated biomarkers or other biomarkers predict ACR50/70 response, EULAR good or moderate response, low disease activity (DAS28 <3.2 or CDAI≤10) or remission (DAS28 < 2.6 or CDAI≤2.8) with subcutaneous abatacept at week 14 and 24 [Time Frame: 14 and 24 weeks]
- Change from baseline in T cell-associated biomarkers or other biomarkers with subcutaneous abatacept at week 14 and 24 [Time Frame: 14 and 24 weeks]
- Adverse event monitoring

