There are markers from other immune cells including macrophages, neutrophils and B cells that could be used to assess inflammation in RA along with T cell markers. Macrophage-associated biomarkers include soluble CD14 (sCD14), soluble CD 163 (sCD163) and calprotectin (S100A8/A9). Both sCD14 and sCD163 are primarily released from macrophages and correlate with disease activity in RA (14, 15). It has been shown sCD14 stimulates pro-inflammatory cytokine production in a manner that is dependent on the TLR4/CD14 membrane complex, NF- κ B and inflammasome (16). Although calprotectin is released from macrophages, the main source is neutrophils, whose cytoplasmic content consists of up to 60% calprotectin. Calprotectin is an endogenous ligand for Toll-like receptor 4 (17) and serum calprotectin levels correlate with synovitis measured by ultrasound (18). It has been reported calprotectin is a predictor of the response to treatments in RA (19). MPO-DNA complexes, a marker of NETosis, a special form of neutrophil death, in which citrullination of RA autoantigens occurs (20), correlate with RA disease activity as demonstrated by us (unpublished data). Other markers are derived from several cell types. Soluble CD25 (sCD25) is a marker for macrophage and T cell activation and the levels of sCD25 decrease in response to abatacept in RA (21). Soluble CD23 (sCD23) is released from activated B cells, monocytes and many other cells and may reflect B cell activity in RA (22,23).

Subsets of CD4 T cells are generated in RA and serum chemokine levels have been used to assess T cell subsets. T helper cell 1 (Th1) pathway is promoted by IL-12 and type I interferon (IFN) and associated with chemokines including CXCL10. It has been shown that type I IFN gene expression signature observed in a subset of RA patients is associated with the response to treatments in RA (24). Therefore, CXCL10, which is shown to correlate with disease activity in early RA (25), could be used as surrogate serum markers for both Th1 cells and type I IFN activities in RA patients.

Recently, PD-1hi CXCR5-T peripheral helper cell (Tph) pathway has been described in synovium of seropositive RA patients (26) as opposed to CXCR5+ T

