8.2. Statistical and analytical methods

The primary endpoint will be the AUC of the receiver operator characteristic (ROC) curves for the biomarkers predicting AC20 response at week 14. We assume that 60% of the patients will respond to abatacept therapy based on the data from the AMPLEx trial (31). Thus, a total sample size of 25 patients will yield approximately 15 responders and 10 non-responders. With this sample, the expected margin of error for 95% confidence intervals for the AUC will be 19% or 22% if the AUC is 0.8, or 0.7, respectively (32). This is a pilot study and the results from this study would be assessed in other cohorts with bigger subject numbers.

For each candidate biomarker, we will compute receiver operating characteristic (ROC) curves related to response rate to abatacept therapy. We will consider a patient to have responded positively to abatacept if they achieve ACR 20 response at week 14.

The area under the ROC curve (AUC) will be the primary measure of the predictive value of the biomarker. Estimates of the AUC's and 95% confidence intervals will be computed for each biomarker. We will also evaluate the predictive value of combinations of any or all baseline biomarker information used in linear risk scores derived using logistic regression models (outcome = response to abatacept therapy). We will evaluate each possible risk-score combination of biomarkers as a predictor by estimating the prediction error using leave-one-out cross-validation (at the 80% specificity cutoff). Similar analyses will be run evaluating the predictive power of the secondary-objective baseline patient characteristics

9. Reference List

2. Dennis G Jr, Holweg CT, Kummerfeld SK, Choy DF, Setiadi AF, Hackney JA, Haverty PM, Gilbert H, Lin WY, Diehl L, Fischer S, Song A, Musselman D, Klearman M, Gabay C, Kavanaugh A, Endres J, Fox DA, Martin F, Townsend MJ. Synovial phenotypes in rheumatoid arthritis correlate with response to biologic therapeutics. *Arthritis Res Ther.* 2014;16(2):R90

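### Low disease activity is an absolute state, so an unadjusted marker AUC for it mixes the marker's link to starting activity with its link to response

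*Combined protocol and SAP*

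**What the plan says.** The secondary endpoints in Section 8.1.2 ask whether baseline markers "predict ACR50/70 response, EULAR good or moderate response, low disease activity" or remission, with the last two given as "low disease activity (DAS28 <3.2 or CDAI≤10) or remission (DAS28 < 2.6 or CDAI≤2.8) with subcutaneous abatacept at week 14 and 24". Both states are defined by where the patient ends up, whatever the starting point.

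Section 4.2, inclusion criterion 6, sets the entry level: "Clinical Disease Activity Index (CDAI) ≥ 16 corresponding to moderate to severe disease activity". No upper limit is given.

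Section 1 (Background and rationale) describes several candidate markers as tracking activity. On two macrophage markers it says "Both sCD14 and sCD163 are primarily released from macrophages and correlate with disease activity in RA". It says the same of MPO-DNA complexes, from unpublished data, and it refers to "CXCL10, which is shown to correlate with disease activity in early RA". No correlation coefficient is given for any of them.

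Section 8.2 makes the AUC the main measure of predictive value: "Estimates of the AUC's and 95% confidence intervals will be computed for each biomarker". The logistic risk scores are built from biomarker information. No baseline-activity covariate, stratification or comparison with baseline activity alone is named. The closing sentence of 8.2 plans similar analyses of baseline patient characteristics, but it does not list them and treats them as predictors, not as adjustment.

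**The concern.** A patient who enters just above the threshold needs a much smaller proportional fall to reach CDAI 10 than one who enters with very active disease. Starting activity can therefore predict low disease activity even when proportional response to abatacept is the same in everyone. A marker that follows starting activity inherits part of that prediction.

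Two errors are possible:

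- A marker with no link to response looks inversely predictive, with low values favourable.
- A marker whose high values indicate both active disease and real benefit has the two effects cancel, and it is dropped.

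In either case the secondary AUC for low disease activity could disagree with the ACR20 result for reasons unrelated to the drug. Section 8.2 intends to carry results into larger cohorts. More patients would narrow the interval but would not remove this component.

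**Working it through.** **1. The plan's own precision figure.** Section 8.2 gives margins of 19% at AUC 0.8 and 22% at AUC 0.7, with 15 responders and 10 non-responders. The Hanley-McNeil formula is SE² = [A(1−A) + (n₁−1)(a−A²) + (n₂−1)(b−A²)] / (n₁n₂), with a = A/(2−A) and b = 2A²/(1+A). With n₁ = 10 and n₂ = 15:

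- A = 0.8: (0.16 + 9×0.0267 + 14×0.0711)/150 = 0.0093; SE 0.0965; 1.96×SE = 0.189.
- A = 0.7: (0.21 + 9×0.0485 + 14×0.0865)/150 = 0.0124; SE 0.1113; 1.96×SE = 0.218.

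Both figures reproduce.

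**2. Required fall, from the documents' cut-offs.** Required fall = 1 − target/baseline.

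| Baseline CDAI | Fall to reach 10 | Fall to reach 2.8 |
|---|---|---|
| 16 | 37.5% | 82.5% |
| 30 | 67% | 91% |
| 50 | 80% | 94% |

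The hurdle for low disease activity varies strongly with baseline. The hurdle for remission is high everywhere and varies much less.

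**3. A marker that only reflects baseline.** The documents give no CDAI distribution, no marker correlation and no relation between baseline and improvement, so all of these are assumptions. Baseline CDAI has mean 25 to 30 and SD 8 to 12, truncated at 16. Fractional improvement has mean 0.45 to 0.55 and SD 0.25 to 0.30. The marker correlates 0.3 to 0.6 with baseline and has no further link to improvement. Low disease activity means follow-up CDAI of 10 or less; DAS28 was not simulated. AUCs take low values as favourable.

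| Correlation of improvement with baseline | Marker AUC | Baseline CDAI alone |
|---|---|---|
| 0 | 0.54–0.61 | 0.65–0.69 |
| 0.2 | 0.51–0.56 | 0.54–0.62 |
| 0.3 | 0.49–0.54 | 0.49–0.57 |
| 0.4 | 0.46–0.50 | 0.44–0.52 |

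In the first row the same marker has AUC 0.50 for a 50% relative improvement. In the other rows that relative-outcome AUC becomes 0.53 to 0.61 with high values favourable, so the contrast between state and relative outcomes also depends on the assumption.

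With higher baselines (mean 28 to 40, SD 8 to 13), mean improvement 50 to 60% (SD 20 to 30%) and independence, the marker AUC is 0.54 to 0.56 at correlation 0.3 and 0.57 to 0.60 at 0.5. Removing the baseline component returns it to 0.50. For remission the marker AUC is 0.51 to 0.56, taking correlations up to 0.7.

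**4. A truly predictive marker.** With correlation 0.5 to baseline and 0.4 to improvement, and improvement independent of baseline, the AUC is 0.68 to 0.69 for 50% improvement. For CDAI of 10 or less it is 0.58 to 0.61, and 0.70 to 0.71 once the baseline component is removed.

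**5. Visibility with 25 patients.** Low disease activity in 25 to 41% gives about 6 to 10 events (25×0.25 = 6.25; 25×0.41 = 10.25). The Hanley-McNeil margin at AUC 0.54 to 0.61 is then about ±0.23 to ±0.27. In three of the higher-baseline scenarios with independence, the chance that the 95% interval excludes 0.5 for a marker that only reflects baseline is 9 to 12% at correlation 0.3 and 12 to 16% at 0.5, against 7 to 8% at zero.

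**6. Candidate remedies with 25 patients.** A Firth logistic model that includes the baseline index removes the bias: mean log odds ratio about 0.02, against −0.26 unadjusted. Comparing leave-one-out AUCs of index plus marker with index alone does not work. Baseline alone averages 0.43 to 0.44, although its apparent AUC was 0.66. Adding a marker with no value beyond baseline gains +0.04 on average, with a 95% range from −0.15 to between +0.45 and +0.50.

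**The case against.** The strongest reply is about size. The shift is a fraction of the sampling margin, and it nearly vanishes if patients who start higher also improve proportionally more. The documents do not say which situation applies. That stands: the direction of the problem is clear, but its magnitude in this study is not established.

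A second reply is that a marker which tracks activity does predict the state, which is literally what the endpoint asks. This also stands, but the stated objective is to predict efficacy of abatacept. A marker that only restates a CDAI already measured adds nothing to that.

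Third, 8.2 defines response only as ACR20 at week 14, so the use of the same AUC for low disease activity is inferred. It is the natural reading, since no other method is given. If it is wrong, the method is unspecified and still needs wording. The baseline characteristics mentioned at the end of 8.2 might include CDAI, which would put its AUC beside the markers', but they are not listed.

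A reader might infer that the ACR20 primary result or ACR50/70 is undermined. The documents do not support that: ACR20 is a separate outcome, and neither it nor ACR50/70 is an attained CDAI or DAS28 cut-off. A reader might also set the AUC of 0.65 to 0.69 for baseline CDAI against the plan's 0.7 planning value and conclude that marker bias is that large. That AUC belongs to baseline CDAI itself; the markers' shift is much smaller.

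**Conclusion.** The concern holds for low disease activity as a secondary outcome. The absolute cut-off, the open-ended entry criterion, the cited marker correlations and the lack of baseline adjustment are all in the documents. The unadjusted AUC there cannot separate starting activity from response.

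The size is modest and rests on assumed inputs: about 0.04 to 0.11 above 0.5 for a marker that only reflects baseline when improvement is independent of baseline, and close to nothing when that correlation is 0.3 to 0.4. Masking of a useful marker is somewhat larger, at roughly 0.07 to 0.11 (0.68 to 0.69, against 0.58 to 0.61). All of this lies within the margin of error with 25 patients. It raises the chance of a false or missed lead; it does not assure one. For remission, 3 to 13% under these assumptions is about 1 to 3 of 25 patients, too few for any adjusted model.

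**What to change.** In Section 8.2, for low disease activity at weeks 14 and 24:

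- Report the AUC of the baseline value of the same index (CDAI for the CDAI definition, DAS28 for the DAS28 definition) beside the marker AUCs.
- Add each marker's odds ratio with 95% interval from a Firth logistic model that includes that baseline value, labelled exploratory.
- Keep the unadjusted AUC as descriptive, and state that it does not separate starting activity from response.
- Do not use a leave-one-out AUC comparison of index plus marker against index alone at this sample size.

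For remission, report descriptively only. The primary ACR20 analysis needs no change for this point.

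The cost is analysis-plan wording; the components of the baseline indices are already collected. The downside is one extra coefficient and wider intervals in a small model.
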